F. STUDY QUESTIONNAIRES AND MEASUREMENT

We chose measures that are based on the conceptual model, have been validated and used widely with minority populations, and have been translated into Spanish; as needed, we will use a translating service with forward and back translation to translate the measures. All items taken from the National Cancer Institute's HINTS survey have been translated. We organize the measures by: primary outcomes, intermediate outcomes, and co-variables.

Primary Outcomes

Participation in colorectal, breast, and cervical cancer screening

We will assess participation in age-appropriate cancer screening behaviors in two ways:

a. Chart Review: Review of electronic medical records at each of the three CHCs.

b. Self-Report: We will ask participants about their participation (yes/no) in specific screening methods: Pap testing (past 3 years), mammography (past 2 years), and colorectal screening (FOBT/FIT, past year; flexible sigmoidoscopy, the past 5 years; and colonoscopy, past 10 years). We will use standardized items from the NCI's HINTS Survey.¹²⁷

Depression

a. Patient Health Questionnaire (PHQ)-9. The PHQ-9 is the 9-item depression module from the full PHQ, and is a well-validated Diagnostic and Statistical Manual of Mental Disorders 4th Edition (DSM-IV) criterion-based measure for screening and diagnosing depressive episode, assessing severity, and monitoring treatment response,^{128,129,130,131} either in person or over the phone.¹³² It has been shown to measure a common concept of depression across racial and ethnic groups, including African Americans and Latinos.^{128,133} Cronbach's alpha was 0.80 in both African American and Latino samples.¹²⁸ As a severity measure, the score can range from 0-27, since each of the 9 items can be scored from 0 (not at all) to 3 (nearly every day). Meta-analysis showed pooled sensitivity of 0.80 and specificity of 0.92 to a diagnosis of major depression among primary care patients in a structured psychiatric interview by a mental health professional using DSM-IV diagnostic criteria.¹³¹ As a practical screening tool, patients with a score of > 10 are considered to have clinically significant depressive symptoms.^{99,134,96,112,135,129}

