b. The Hopkins Symptom Checklist (SCL-20). The SCL-20 consists of the 20 depression items on a 4-point scale from the SCL-90, and has been shown to be a valid and reliable measure of depression in diverse outpatient and community populations (Cronbach's alpha = 0.87; test-retest r=0.81).^{136,137} It has been shown to be sensitive to change in studies of collaborative care in primary care settings^{99,97,121,96,112,134,135} and among minority group patients.^{95,99,133}

We will consider clinically meaningful improvement of depressive symptoms to be a > 50% reduction in baseline SCL-20 or PHQ-9, and depression remission as an SCL-20 score <0.5 or a PHQ-9<5.

Intermediate Outcomes

Quality of Life/Health Status. We will measure quality of life with the Medical Outcomes Study (MOS) Short Form Health Survey (SF-12), which includes heterogeneous items from the SF-36 physical and mental component scales. This general measure of health status assesses the patient's perceived health status and whether health problems interfere with normal functioning. The SF-12 has with demonstrated validity and test-retest reliability in the general population and in patients with chronic health conditions, and has been tested in five languages, including Spanish.¹³⁸ It has been used extensively as a quality of life measure in collaborative care studies,⁴² including with low-income minority populations.^{95,99} It has also been used frequently in screening studies, for cancer and other conditions.¹³⁹⁻¹⁴² The SF-12 has been validated as an indicator of effects of depression on quality of life in ethnically diverse patients.¹⁴³

Mental Health Care Utilization.

We will assess mental health care utilization in two ways:

c. Chart review. We will use data from the electronic medical record to determine the number of health visits, and the kind of provider seen for mental health care (psychiatrist, psychologist, and/or clinical social worker).

d. Patient report. At baseline, we will ask respondents how many times in the past six months they have seen a provider to talk about or get medication for feeling sad, nervous, hopeless, or blue. In addition, we will ask participants about their ability to arrange to get mental health treatment, as well as whether they

have the financial resources to access mental health services. These questions will be adapted from the NCI's HINTS survey.¹²⁷

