To determine whether reducing depression increases the likelihood that low-income women will receive age-appropriate cancer screening (Aim 3), we included improvement in depression (as well as depression remission in a separate model) in the logistic regression models to examine its association with cancer screenings, and also to examine if the difference between the two intervention arms was modified by change in depression; we examined the interaction between improvement in depression and treatment (as well as depression remission and treatment). To determine whether the effectiveness of the CCI intervention varies according to patient characteristics, such as language spoken and, obesity, etc. (Aim 4), we examined each of these variables as possible effect modifiers. However, it is understood that the statistical power for testing an interaction term may be limited in this study; consequently, this aim was treated as exploratory and the results of this study will be used to design a future, more definitive study with interventions identified and targeted to address issues associated with specific subgroups who may experience reduced benefit from the intervention.

Missing Data

Missing data are a common problem in longitudinal studies. In the context of the present study, missing data will occur when, for example, not all the screening outcomes are reported for a given participant, or some of the co-variables (e.g., body mass index) are missing. For the initial approach in the primary analysis of the study, study participants with missing values on either the outcomes or the co-variables were first removed from the study for the evaluation of intervention effects. However, this approach required the assumption of missing completely at random to be true. A violation of this assumption may lead to bias in the estimate of the intervention effect. We first examined the level of missing data by each outcome and each co-variate in the model. If the rate of missing data is small (<5%), the chance that it will bias the result is very low; however, if the rate of missing data is moderate (>10%), sensitivity analysis was used to examine the robustness of the result. For example, if one variable has a moderate level of missing, we conducted a sensitivity analysis which compared those participants with the remaining participants and also included those participants in the analyses by adding a separate missing category.

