Heterogeneity of Treatment Effects (HTE) Analysis

A potential problem in intervention studies is heterogeneity within the participant population. To examine whether the effectiveness of intervention varies according to patient characteristics, here we focused on BMI and primary language as previous evidence supported that these two characteristics affected the likelihood of being up to date with cancer screening. In addition, because women who were up to date at baseline may be very different from women who were not up to date at baseline, we examined the subset of women who were not up to date for each specific cancer screening and examined if the intervention improved their up to date screening status.

Sample size/Power Calculation

The primary aim of the study was to compare the effectiveness of the Collaborative Care Intervention (CCI) versus Prevention Care Management (PCM) to increase participation in screenings for cervical cancer, breast cancer and colon cancer among women with depression. Women were equally randomized to the two intervention arms. With 356 women in each arm, the study had about 80% power to detect a minimum 10% difference between two arms in cancer screening participation with a two-sided type I error rate of 5%, under various assumptions of screening rate for the PCM (control) group. This 10% difference is considered the smallest difference of interest, based on previous studies comparing the PCM to Usual Care.^{1, 2,3} Therefore, with 356 women with complete data per intervention arm (n=712) our study had sufficient power to detect a clinically meaningful difference between the two intervention arms.

Multiple Comparisons

We evaluated three separate screening outcomes (for cervical cancer, breast cancer and colorectal cancer) so that multiple hypothesis testing would be involved. However, the relative importance of factors contributing to participation in each screening test varied between tests, and we were interested in comparing the two intervention arms for each test separately, as well as globally for all three tests. We also examined a summary of cancer

screening outcome across three types of cancers by comparing the total number of up to date cancer screenings at the follow-up between the two treatment arms, using a regression model for ordinal outcome. Since these statistical tests were hypothesis-driven rather than exploratory, we did not think multiple comparison adjustment for type I error rate was necessary.

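### Aim 3 relies on undefined improvement and remission variables; the only definitions are yes/no cuts of graded depression scales, and no model uses the scores themselves

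*SAP*

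**What the plan says.** The SAP section on moderators and mediators describes Aim 3 in one sentence: "we included improvement in depression (as well as depression remission in a separate model) in the logistic regression models". Each variable is then interacted with arm. The sentence also speaks of effect modification by change in depression, without naming a scale, a visit or a coding. Improvement and remission are not defined anywhere in the SAP.

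The definitions are in the protocol, Section F, under the depression outcome: "We will consider clinically meaningful improvement of depressive symptoms to be a > 50% reduction in baseline SCL-20 or PHQ-9". Remission is defined there as SCL-20 below 0.5 or PHQ-9 below 5. The same section describes the PHQ-9 as a graded measure: "As a severity measure, the score can range from 0-27". The SCL-20 has 20 items on a 4-point scale. Under Section C, self-report measures are collected at all three interviews (baseline, 6 and 12 months).

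For comparing arms on continuous outcomes, the SAP's intention-to-treat section provides a t-test and linear regression. It describes nothing comparable for Aim 3.

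**The concern.** A responder definition is a sensible way to report how many women did well in each arm. It is a coarse way to measure the exposure in a mechanism analysis, because every woman on the same side of the cut is treated as identical.

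Aim 3 asks whether lowering depression is how the collaborative care arm raises screening. If depression enters only as two indicators, the association with screening is estimated with less information than the data hold, and so is the interaction with arm. A null Aim 3 result could then reflect the coding and not the absence of the mechanism. This would remain true even if confounding, time order and the estimation of an indirect effect were all handled well.

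**Working it through.** **1. The plan's own power figure.** The SAP's sample-size section says "With 356 women in each arm, the study had about 80% power to detect a minimum 10% difference between two arms", at two-sided 5% and "under various assumptions of screening rate for the PCM (control) group". For control rate p, with a pooled standard error (SE) under the null and no continuity correction, power = Φ[(0.10 − 1.96·SE₀)/SE₁]. At 30% versus 40%:
- SE₀ = √(2×0.35×0.65/356) = 0.0358
- SE₁ = √((0.21+0.24)/356) = 0.0356
- power = Φ(0.84) = 80%

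Across control rates from 10% to 80%, power is lowest near 45% (76.2%) and is 80.0% at 30% and at 60%. The figure reproduces, but it concerns the arm comparison of screening. The documents give no power, effect size, SD, improvement rate or remission rate for Aim 3.

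**2. What the cuts do, from the documents' rules alone.** Entry requires PHQ-9 of at least 8 (Section G). Judged on PHQ-9:

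| Baseline → follow-up | Fall | >50% improved? | Remitted (<5)? |
|---|---|---|---|
| 20 → 10 | 10 points, 50% | no | no |
| 8 → 4 | 4 points, 50% | no | yes |
| 8 → 3 | 5 points, 62.5% | yes | yes |

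A 10-point fall is coded with the women who worsened, while a 5-point fall counts as success on both variables.

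**3. General size of the loss.** For a normal predictor with a linear effect, cut so that a share q lies on one side, information kept = φ(z_q)²/[q(1−q)]. If the continuous analysis has 80% power (1.96 + 0.84 = 2.80), power after the cut = Φ(2.80·√info − 1.96).
- q = 50%: 0.399²/0.25 = 0.64; power 61%
- q = 40%: 0.62; power 60%
- q = 30%: 0.58; power 57%
- q = 20%: 0.280²/0.16 = 0.49; power 50%

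The losses are 19, 20, 23 and 30 points. If the continuous analysis had 99% power, they would be about 6, 7, 9 and 14 points.

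**4. Simulation at n=712, linear effect of change.** Assumed, not in the documents: follow-up SD 6, correlation with baseline 0.4, mean improvement 4 or 6 points, arm effect 1.5 points, 50% screened. These give 32% to 46% improved and 20% to 31% remitted. There were 800 replicates per setting; the model was screening on arm plus one depression variable. Ranges cover the two mean improvements.

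| Odds ratio per SD of change | Continuous change | >50% improved | Remitted | Loss, improved | Loss, remitted |
|---|---|---|---|---|---|
| 1.1 | 23–26% | 16% | 11% | 7–10 | 12–15 |
| 1.2 | 67–69% | 41–43% | 26–28% | 26 | 41 |
| 1.25 | 84–85% | 56–60% | 34–39% | 25–27 | 45–50 |
| 1.3 | 92–95% | 70–72% | 45–49% | 22–23 | 47 |
| 1.5 | about 100% | 97% | 78–82% | 3 | 18–22 |
| 1.8 | 100% | about 100% | 97–98% | 0 | 2–3 |

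Losses can exceed those in step 3 because neither cut is a cut of absolute change: one depends on the baseline score and the other on the follow-up level.

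**5. Follow-up score with baseline as covariate.** A second set of assumptions was used: baseline mean 13.9, SD 3.9, entry at 8 or above; follow-up SD 4.9; correlation 0.49; 28% improved; 17% remitted. Power for the continuous score, improvement and remission was:
- screening depends on absolute change: 65%, 40%, 22%
- screening depends on follow-up level: 69%, 53%, 46%
- screening depends on percent change: 68%, 44%, 35%

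**6. When the cut is right.** If screening truly steps at 50% improvement, the order reverses. Under the step 4 assumptions with mean improvement 5 and an odds ratio of 1.5 for improved versus not, power is 72% with the indicator and 47% with continuous change. Under the step 5 assumptions it is 75% versus 52%.

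**The case against.** Response and remission are clinical states that the protocol defines, and asking whether women who reach them get screened is a fair question. Aim 3 is not the powered aim. The SAP does not say that improvement is a yes/no variable: the protocol's definition is of clinically meaningful improvement, a qualifier the SAP omits, and the SAP also refers to change in depression. All of this stands. The yes/no coding of improvement is an inference from the only definition available; remission is a threshold in any case. If a continuous variable was intended, the SAP still needs to say so.

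Two stronger readings are tempting, and the documents support neither.

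A reader might infer that the coding costs this trial a fixed amount of power, for instance the 16 to 43 points spanned by the linear settings in step 5 (69 − 53 and 65 − 22). Those settings have 65% to 69% continuous power, in the region where the loss is large. The documents give no effect size from which to choose a row of the table in step 4.

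A reader might also infer that a stated share of a mediated arm effect would go unexplained. In very large simulated samples with full mediation through continuous change, 35% to 45% of the arm log-odds ratio remained after adjusting for improvement and 57% to 66% after adjusting for remission. However, the SAP specifies an association and an interaction, not a comparison of the arm coefficient before and after adjustment. At n=712 and 50% screened, the SE of the arm log-odds ratio is about √(2/(356×0.25)) = 0.15. The largest total effect simulated was 0.305, which leaves about 0.62×0.305 = 0.19 after adjusting for remission, or 1.3 SE. Most settings leave far less, so the trial could not resolve the residual.

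**Conclusion.** The point holds as a fault of specification and efficiency. Aim 3 rests on two variables that the SAP leaves undefined and the protocol defines only as cuts, with no model that uses the scores.

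The size is conditional. The 49% to 64% of information kept assumes a normal predictor, a linear effect and splits of 20% to 50%. The loss of about 0 to 50 points at n=712 assumes the PHQ-9 distributions listed above. It is largest for modest effects (odds ratios of about 1.2 to 1.3 per SD), small for improvement at 1.5 and for both cuts at 1.8, and it changes sign if the cut itself drives screening. No interaction power was simulated. The information argument applies to the interaction too, but no figure is claimed for it. The SAP's remark about limited interaction power is made for Aim 4 and does not cover this.

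**What to change.** In the SAP's Aim 3 paragraph:
- State how improvement is coded, on which scale and at which visit.
- Make the leading model the logistic regression of screening on arm and the continuous follow-up PHQ-9 score, with the baseline PHQ-9 score as covariate. Run the same model separately for SCL-20.
- Add a spline or quadratic term as a nonlinearity check. This also guards against a true step at the cut.
- Use the same continuous term in the interaction with arm.
- Keep >50% improvement and remission as secondary versions, using the protocol's definitions.

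The cost is SAP wording and a rerun on data already collected. The odds ratio becomes one per scale point or per SD, which is less immediate to clinicians than improved versus not improved, and linearity has to be checked. Because the SAP is written largely in the past tense, the report should say whether the continuous model was added after Aim 3 results were seen.

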For the integrated intervention, or “intervention package”⁸⁶ that combines screening and depression care management, we will adapt the evidence-based Three Component Model (TCM) of collaborative care,^{97,98,57} and we will incorporate additional evidence-based socio-cultural collaborative care elements developed by Ell and colleagues.^{95,99} TCM, funded as part of the MacArthur Foundation Initiative on Depression and Primary care, provides a system for depression management as recommended by the U.S. Preventive Services Task Force, and its structure is complementary to that of PCM. Components include telephone care management, collaboration between mental health and primary care professionals, and preparation of primary care clinicians and practices to provide systematic depression management through training. Based on Ell’s successful collaborative care trials with low-income Hispanic populations^{95,99} we will draw on her work to add the following elements to TCM: 1) psychoeducation to dispel treatment misconceptions, reduce stigma associated with depression, and enhance the therapeutic alliance; and 2) patient navigation assistance specifically to facilitate patient self-efficacy, patient-provider communication, access to financial and social resources, with a focus on specific behavioral activities to complete screening examinations and follow-up (e.g., scheduling appointments, reminders, transportation).

Outcomes include: reduced depression, improved quality of life, improved satisfaction with healthcare decisions, increased self-efficacy, decreased internalized stigma, and decreased likelihood of morbidity and mortality from breast, cervical, and colorectal cancer.

Main Hypotheses

Our hypothesis that the 12-month CCI intervention we will implement at the six participating sites will be significantly more effective than the PCM comparison condition in improving key patient-reported outcomes associated with cancer screening and depression, including cancer screening knowledge and attitudes, self-efficacy, depression-related stigma, provider referrals, participation in mental health care, medication adherence, quality of life, and satisfaction with care and treatment decisions, and depression (**Aim 1**).

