We expect the intervention to have a positive impact on screening participation itself (**Aim 2**) by reducing depression (**Aim 3**) and by influencing patient-reported outcomes associated with screening. Finally, as shown, we hypothesize that the effectiveness of CCI in comparison to the PCM condition in increasing screening may vary depending on patient characteristics, such as duration of depression, presence of other chronic conditions, obesity, personal experience with cancer, and demographic characteristics (**Aim 4**); we also hypothesize that depression outcomes will vary according to these patient characteristics as well. We recognize that change has both intended and unintended consequences and is not linear. However, our model depicts the hypothesized pathways for the study and analysis as described; any additional analyses of bi-directionality will be exploratory.

To determine the effectiveness of the CCI intervention in increasing cancer screening over a one-year period, we will compare it to the performance of the traditional PCM cancer screening intervention among depressed women who are non-adherent with one or more screenings. Because PCM has demonstrated effectiveness among health center patients of the Bronx in general, such a comparison will be an ideal test of whether addressing and reducing depression are necessary steps to increase rates of screening among low-income depressed women. Utilizing a “usual or standard care” group as the comparison condition instead of the PCM intervention would make it impossible to isolate the effect of adding the depression reduction collaborative care components to PCM. Moreover, because PCM has already been demonstrated to be effective our MHC Connection partnership felt that offering PCM as the comparison condition would be the most ethical approach. If we find that PCM alone works just as well among depressed women as our new, integrated CCI intervention – i.e., if our findings do not enable us to reject the null hypothesis – this too has important implications for the delivery of patient-centered screening interventions in the Bronx and in other areas with a high density of low-income minority populations.

Intervention Content

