Eligible women will be invited to participate in the study. When recruitment is conducted in person, the care manager will make every effort to complete the consent process at that time, and she will also attempt to complete the 45-minute baseline structured interview, described below. If this is not possible, the care manager will schedule another appointment, as soon as possible, to conduct the baseline interview by phone or in person at the CHC. Based on prior collaborative care research with minority patients in these Bronx CHCs and other similar settings, we expect a consent rate of about 70%.^{76,99} In keeping with PCM and other collaborative care research,^{76,112} we will use a randomized block algorithm, stratified by CHC to assign women to the PCM control arm or the CCI intervention arm. Block size will be allowed to vary randomly to preclude any exercise of judgement, or bias, in the allocation of participants to specific arms. Study participants will be randomized 1:1 to each of the two arms, according to a scheme prepared by the study statistician, who is not onsite at any of the CHCs. Randomization will occur after the baseline interview; women in the study will be notified of their assignment at the time of the first call with the care manager. [name], study data coordinator, will disclose the block randomization process and will inform care managers of the assignments. [name], Project Director, will supervise [name] and all aspects of data collection described below.

Initial phone contact

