Colonoscopy) were compared separately between the two intervention arms using a chi square test comparing two independent binomial proportions (Aim 1). Next, logistic regression was used to control for potential confounders, including the factors discussed that were identified as being unevenly distributed between the CCI and PCM intervention arms at baseline. To account for possible differences by site, site indicators were included in the model as a fixed effect to examine if there were potential confounders; if they were not found to be confounders, they were removed from the model. A combined ordinal cancer screening outcome, calculated as number of up to date cancer screening tests (which vary from 0 to 3) was analyzed using the proportional odds model (PROC GENMOD in SAS). Other key patient-reported outcomes, including changes in depression, self-efficacy, stigma, satisfaction with cancer screening decision and satisfaction with care, and quality of life, were also compared between the two intervention arms (Aim 2). For continuous outcomes, a two-sample t-test was used to examine the difference between the two arms, and a linear regression model was used to control for potential confounders; for categorical outcomes, a chi-square test was used to examine the difference between the two arms and a logistic regression (for binary outcome) or a multinomial logistic regression (for a categorical outcome with more than two levels) was also used to control for potential confounders.

Multivariate analyses testing for moderators and mediators

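### Aim 3 treats depression improvement and remission, which arise after randomisation and which CCI is meant to change, as modifiers of the arm difference in screening

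*SAP*

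**What the plan says.** The SAP section on moderators and mediators has two parts for Aim 3. Improvement in depression (remission in a separate model) enters the logistic regression for screening as a predictor. The same models are then used "to examine if the difference between the two intervention arms was modified by change in depression", and the SAP adds that "we examined the interaction between improvement in depression and treatment (as well as depression remission and treatment").

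Other places fix the status of these two variables:

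- **Definition.** Protocol section F takes "clinically meaningful improvement of depressive symptoms to be a > 50% reduction in baseline SCL-20 or PHQ-9". Remission is an SCL-20 below 0.5 or a PHQ-9 below 5.
- **Timing.** Protocol section C schedules interviews at baseline, 6 and 12 months and states: "Randomization will occur after the baseline interview". Improvement and remission are therefore known only after allocation.
- **Target of treatment.** The protocol's outcome list in section B begins "Outcomes include: reduced depression, improved quality of life". Its hypotheses expect CCI to raise screening "by reducing depression (Aim 3) and by influencing patient-reported outcomes associated with screening". The SAP's ITT section compares arms on "Other key patient-reported outcomes, including changes in depression, self-efficacy, stigma", so change in depression is itself an outcome.

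The SAP names no mediation estimator, no set of confounders for the relation between depression and screening, and no caution about conditioning on a post-randomisation variable. Its exploratory label follows the Aim 4 sentence and refers to a single aim.

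**The concern.** A statement that the arm difference is modified by some variable invites the reader to compare CCI with PCM at each level of that variable. Randomisation protects that comparison when the variable is fixed at baseline. It does not protect it here. If CCI lifts depression in women who would have stayed depressed under PCM, those women count as improvers in one arm and non-improvers in the other. If their tendency to be screened differs from that of other women, the product term picks up the difference in case mix, whatever CCI does to screening.

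The protocol asks whether reducing depression is a necessary step towards screening in this population. A significant product term could be taken as an answer to that question although the data would not support one. A null term could be taken as evidence against it when selection had hidden a real interaction.

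The concern is with the effect-modification reading of the product terms. It does not extend to the use of improvement as a predictor when the question is mediation.

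**Working it through.** **1. The plan's own figure.** The SAP gives 356 per arm for about 80% power, a 10-point difference and two-sided 5%. At 30% v 40%:

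n = [1.96·√(2·0.35·0.65) + 0.8416·√(0.30·0.70 + 0.40·0.60)]² / 0.10² = (1.3221 + 0.5646)² / 0.01 = 356.

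The figure reproduces. It concerns the main arm comparison. The plan gives no power or error rate for the Aim 3 interaction, so 356 per arm is used below as the analysed number.

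**2. Closed-form example with no CCI effect on screening in any woman.** Divide women into A (improve under either arm), C (improve only under CCI) and N (improve under neither). Assumed shares are 30%, 20% and 50%, which makes improvement 30% in PCM and 50% in CCI. Assumed screening rates are 60%, 30% and 30%, identical in both arms.

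- Improvers, CCI: (0.30·0.60 + 0.20·0.30)/0.50 = 48%. Improvers, PCM: 60%.
- Non-improvers, CCI: 30%. Non-improvers, PCM: (0.20·0.30 + 0.50·0.30)/0.70 = 30%.
- Odds ratio in improvers: (0.48/0.52)/(0.60/0.40) = 0.62. In non-improvers: 1.00. Ratio of odds ratios: 0.62, log −0.486.
- Cell sizes are 178 and 178 (CCI) and 106.8 and 249.2 (PCM). Variance of the log ratio = 1/(178·0.48·0.52) + 1/(106.8·0.60·0.40) + 1/(178·0.30·0.70) + 1/(249.2·0.30·0.70) = 0.1074; SE 0.328.
- z = −0.486/0.328 = −1.48. A two-sided 5% Wald test rejects in Φ(−1.96 + 1.48) ≈ 32% of trials. Simulation gave 33.5%.

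Other assumed screening rates, same shares, still no CCI effect:

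| Rates A/C/N | Ratio of odds ratios | Rejection |
|---|---|---|
| 50/25/50% | 0.50 | 59% |
| 60/30/30% | 0.62 | 32% |
| 45/30/45% | 0.66 | 26% |
| 50/50/30% | 1.30 | 13% |
| 60/45/30% | 0.95 | 5% |
| equal in all | 1.00 | 5% |

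Because CCI does nothing here, the false interaction is not merely a product of the odds-ratio scale. With C only 10% of women, the first four rows give 7% to 24%.

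**3. A second model.** An unmeasured trait (standard normal) raises screening by 1 log-odds per SD. It also predicts improvement, with a slope that may differ by arm. Improvement itself has no effect on screening, and CCI's effect is constant in log-odds. Improvement is 30% in PCM and 50% in CCI. The SAP states no PCM screening rate, so 30% to 60% was used.

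| Trait slope for improvement, CCI v PCM | Rejection of the interaction | Apparent effect when the true overall effect is 10 points |
|---|---|---|
| 1.0 v 1.0 | 5% | 5.8 to 7.6 in both strata |
| 0.5 v 0.3 | 7–8% | about 11 (improvers), 7 (non-improvers) |
| 1.0 v 0.5 | about 15% | not needed here |
| 1.0 v 0.3 | 27–30% | 14.5 and 3.1 at a PCM rate of 40% |
| 0.3 v 1.0 | 28–32% | about 1 and 12 |
| 1.0 v 0 | about 60% | not needed here |

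With slopes 1.0 v 0.3 and no CCI effect at all, the strata show about +4 points in improvers and −6 to −7 in non-improvers. With improvement at 40% v 30% and the trait's effect on screening halved to 0.5, slopes of 1.0 v 0.3 give 12% rejection and 0.5 v 0.3 give 6%.

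**The case against.** The best defence is that Aim 3 is a mediation question. The section heading names mediators, the protocol draws a path from CCI through depression to screening, and an exposure-by-mediator product is a standard term in such a model. This stands: the term need not be deleted. What fails is the purpose the SAP gives it, together with the lack of a mediation model around it.

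Four stronger readings are tempting, and the documents do not support them.

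- *The trial will report CCI effects separately in improvers and non-improvers.* The SAP announces only that the interaction was examined. Stratum-specific effects are a risk to guard against and are not a planned output.
- *The error favours CCI among improvers.* Reversing the assumed slopes reverses the sign, and nothing in the documents fixes the direction.
- *The test is invalid whenever CCI changes depression.* With equal slopes it keeps 5% despite 50% v 30% improvement, and two of the six no-effect scenarios in the first table show no inflation worth the name.
- *A post-randomisation variable can never enter a modification question.* A principal-stratum analysis is a recognised route, but it needs assumptions that the SAP does not make.

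A further defence is that the work is exploratory. That label is attached to Aim 4, and the reason given is low power. Low power does not excuse bias.

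Finally, the SAP is written in the past tense, so the analysis may already have been run. That limits the remedy largely to labelling and interpretation, which can still be corrected.

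**Conclusion.** The concern holds in this form. Improvement and remission are post-randomisation variables that CCI is built to change, so their products with arm do not test whether the randomised arm difference is modified. An interaction can appear, or be hidden, when CCI's effect is the same in every woman.

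Under the stated assumptions the false interaction rate runs from 5% to about 60%, and its sign is unknown. Arm contrasts within improver strata can be off even when the test holds its level: about 6 to 8 points where the truth is 10. The improvement rates, the trait strengths and the PCM screening rate are all assumed. The documents give none of them, so the range shows what is possible and is not a forecast for this trial.

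The reach is limited to the Aim 3 product terms. A reader might infer that the main screening result or the 356 per arm is in doubt. Neither depends on these terms, and the Aim 4 analyses use patient characteristics to which this objection does not apply in the same form.

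**What to change.** In the SAP section on moderators and mediators:

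1. Remove the statement that the arm-by-improvement and arm-by-remission terms test whether the arm difference is modified by change in depression.
2. Keep the products only as exposure-mediator interactions within an Aim 3 mediation model. Adjust that model for baseline depression and for other baseline predictors of both improvement and screening. Label it non-randomised and exploratory.
3. State that no arm contrast within improvers or non-improvers will be presented as a treatment effect.
4. Restrict effect-modifier tests to baseline variables. Arm by baseline PHQ-9 or SCL-20 may be added under exploratory Aim 4. It asks whether initial severity matters, which is a different question from Aim 3, and entry at PHQ-9 of 8 or more narrows its range. It is an option and does not replace the Aim 3 analysis.

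The cost is a few sentences of SAP text and one specified model, with PHQ-9 and SCL-20 already in the baseline interview. If the analysis has been run, the mediation model should be reported as post hoc and the existing interaction results as descriptive. The trial gives up a modification claim that these terms could not support.
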